4.4.3 Study Endpoints

The primary safety endpoint is freedom from major adverse events (MAE) at 30 days or during hospitalization if this exceeds 30 days.

Major adverse events include death, bowel ischemia, myocardial infarction, paraplegia, renal failure, respiratory failure, and stroke.

The primary effectiveness endpoint is the proportion of the study subjects with treatment success at 1 year. Treatment success is defined as a composite of technical success and freedom from the following:

- Aneurysm enlargement i.e., greater than 5mm as compared to any previous CT measure using orthogonal (i.e., perpendicular to the centerline) measurements
- Aneurysm rupture
- Aneurysm-related mortality
- Conversion to open repair
- Secondary intervention for migration, Type I and III endoleaks, device integrity failure (e.g., fracture), and patency-related events (i.e., device component stenosis or occlusion and embolic events)

Secondary endpoints include:

- Technical success and the individual components of technical success:
 - Successful delivery
 - Deployment at the intended implantation site
 - Patency of all endovascular graft and stent components
 - Absence of device deformations requiring unplanned placement of an additional device
 - Absence of inadvertent covering of aortic branch vessels
 - Successful withdrawal

- Freedom from the individual components of the primary safety endpoint at 30 days:
 - Death
 - Bowel ischemia
 - Myocardial infarction
 - Paraplegia
 - Renal failure
 - Respiratory failure
 - Stroke
- Freedom from paraparesis at 30 days
- The following at each follow-up interval:
 - Treatment success and the individual components of treatment success including freedom from the following:
 - Aneurysm enlargement
 - Aneurysm-related mortality
 - Aneurysm rupture
 - Conversion to open repair
 - Secondary intervention for migration, type I and III endoleaks, device integrity failure (i.e., fracture), and patency-related events (i.e., device stenosis or occlusion and embolic events).
 - Renal failure
 - All-cause mortality
 - Endoleaks
 - Device integrity failure (e.g., fracture)

- Patency-related events (i.e., device stenosis or occlusion and embolic events)
- Other device-related events

4.4.4 Follow-up Schedule

Patients included in the study will undergo follow-up at one month, six months, twelve months and then annually for five years. In the event of patient death, an autopsy may be performed.

Table 5. Follow-up Table

	Pre-op	Intra-op Index	Pre-discharge	Intra-op Completion (if staged)	Pre-discharge (if staged)	Month						
						1	6	12	24	36	48	60
CTA/CT with contrast of Chest, Abdomen, and Pelvis	X ^{2,3}		X ^{1,2, 8}		X ^{1,2, 8}	X ^{1,2}	X ^{1,2}	X ^{1,2}	X ^{1,2}	X ^{1,2}	X ^{1,2}	X ^{1,2}
Angiography	X ³	X										
Blood Tests	X ⁴	X ^{5, 6}	X ^{4, 8}	X ^{4,6}	X ^{4, 8}	X ⁴	X ⁴	X ⁴	X ⁴	X ⁴	X ⁴	X ⁴
Clinical Exam (including ABI)	X ⁷		X ⁸		X ⁸	X ⁷	X ⁷	X ⁷	X ⁷	X ⁷	X ⁷	X ⁷
Branch Patency (duplex ultrasound)						X ²	X ²	X ²	X ²	X ²	X ²	X ²

1 Device X-ray may be requested to provide more focused imaging if potential device integrity issues are identified, but are unable to be confirmed, using CT.
2 If renal function does not allow for CTA or CT with contrast, an alternative contrast-enhanced imaging modality or, at a minimum, non-contrast CT in conjunction with duplex ultrasound may be used at physicians discretion.
3 Pre-procedure angiography may be requested at discretion of film reviewer.
4 Blood tests include CBC for hemoglobin and BMP for creatinine.
5 Blood test for ACT.
6 Other intra-op labs for anesthesia.
7 Urine pregnancy test (for female patients of childbearing age).
8 CT, Duplex, ABI and labs are optional at the pre-discharge and one month visits between staging procedures.

4.4.5 Patient Enrollment and Screening

The investigator will assess potential study subjects with thoracoabdominal aortic aneurysms for their suitability for enrollment into the clinical study. If the patient appears to meet eligibility

criteria, then the investigator or clinical study coordinator will discuss the study with the patient and provide patient education materials to adequately inform the patient of potential risks and benefits, required follow-up procedures, and answer any questions. The clinical study coordinator will facilitate the informed consent process. After the patient has been properly consented, the patient will complete additional screening procedures that need to be completed. If the patient does not sign the informed consent, they will not be enrolled in the study. Information to be collected for screening include:

- Patient demographics
- Medical history
- Current health status
- Physical examination
- Ankle Brachial Index (ABI)
- Pregnancy test (for female patients of childbearing age)
- An X-Ray may be performed per local standard of care. A/P, Lateral and Bilateral Oblique Images will be obtained.
- CTA or CT with contrast of the chest, abdomen and pelvis if renal function allows. If renal function does not allow CT with contrast, an alternative contrast-enhanced imaging modality or, at a minimum, CT non-contrast in conjunction with Duplex ultrasound will be used at physician discretion to evaluate:
 - Access vessels for compatibility with vascular access techniques
 - Obstructive stenting of the visceral vessels
 - Vessels diameters suitable for use with the VTAAA stent graft system
 - Aneurysm rupture
 - Branch stenosis of the SMA, celiac, left and right renal arteries

- Dissection
 - Patency of left subclavian artery, hypogastric arteries, lumbar arteries, and all four visceral vessels
 - Thrombus or excessive calcification in the neck of the aneurysm
 - Presence and location of any previously placed graft material
- Complete blood count to evaluate white blood cells, hemoglobin, and platelets
 - Basic metabolic panel to evaluate creatinine
 - Pulmonary function test (for patients with a history of smoking or if deemed necessary by the PI)
 - Cardiac clearance

4.4.5.1 Case Planning

From the pre-op CT, the surgeon will make the following measurements to size the endografts.

1. Length of the proximal seal zone, the distance required to land the thoracic bifurcation stent graft, this requires greater than or equal to 2.5 cm section of healthy aorta, distal to the left subclavian artery.
2. Diameter of the proximal landing zone to define the required diameter of the thoracic bifurcation stent graft. The diameter of the thoracic bifurcation stent graft should be 10-15% larger than the diameter of the aorta to properly oversize the stent graft.
3. Maximum aortic diameter within the treated aorta
4. Distance from the top of the celiac to the top of the most cephalic renal.
5. Distance from the top of the proximal seal zone to the takeoff of the celiac.
6. Distance from the top of the celiac to the SMA.
7. Angulation at the mid-thoracic aorta.

8. Angulation at the diaphragm.
9. Angulation at the renal arteries.
10. Distance from the right renal to the ipsilateral internal iliac artery.
11. Distance from lower renals to aortic bifurcation.
12. Diameter of the branch vessels (celiac, SMA, left renal, and right renal) to determine the diameter bridging stents needed and percent patency.
13. Diameter of the right and left common iliac to secure the distal seal of the infrarenal bifurcation.
14. Diameter of the distal aorta to secure the distal seal in the aorta
15. Length between distal edge of LSA and start of aneurysm
16. Length of proximal seal zone
17. Length of aneurysm
18. Minimum diameter of the access sites (right and left femoral and brachial access site).
19. Length from the access sites to the target treatment zone (right and left femoral and brachial access site).

Note: If treating a dissection under the expanded selection arm the true and false lumen as well as any naturally occurring fenestrations will be evaluated to determine placement of the device and which lumen feeds the branch vessels.

Note: If treating a patient with previously placed graft material, either proximally or distally, it must be determined if the landing zones will be within the previously placed graft material or if the landing zones extend beyond the limits of the previously placed graft material.

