3.6 Device Description and Drawings

The VTAAA stent graft system is made up of two main body components and makes use of several off-the-shelf FDA-approved stent graft components (see Appendix B) for system drawing). The two custom main body grafts are the thoracic bifurcation (Figure 1A) and the visceral manifold (Figure 1B). The thoracic bifurcation is deployed in the thoracic aorta and provides the proximal seal for the device. For a Type I or II thoracoabdominal aneurysm the proximal seal is in zone 3 and for Type III and V the device seals in zone 4. The smaller 16 mm limb of the thoracic bifurcation extends to the infrarenal segment to either seal in zone 9 for a Type I and V and in zone 10 for Type II and III. The two limbs of the thoracic bifurcation allow for continued aortic flow while deploying the visceral segment. The visceral manifold is deployed within the larger 20 mm limb of the thoracic bifurcation to set the stage for the visceral debranching. The branches of the visceral manifold extend to the visceral vessel with the use of covered bridging stents and provide distal seal of the manifold. The smaller 16 mm limb of the thoracic bifurcation extends to the infrarenal segment to either seal in zone 9 for a Type I and V and in zone 10 for Type II and III. All other connections in the device make use of sizes that are modular and independent of patient anatomy.

Figure 1: VTAAA Stent Graft System

Aortic components

The thoracic bifurcation stent graft (Medtronic) seals to the native aorta/healthy tissue and bifurcates blood flow in the descending thoracic aorta. The distal end bifurcates into two smaller legs (20 mm and 16 mm) suitable for modular connection to the visceral manifold stent graft and the visceral bypass stent graft. The thoracic bifurcation is composed of a self-expanding, metallic spring scaffold made from nitinol stents sewn to a polyester fabric graft with nonresorbable sutures and is manufactured in the following sizes:

Proximal Diameter (mm)	Target Vessel Diameter Range (mm)	Visceral Perfusion Manifold Diameter (mm)	Visceral Bypass Diameter (mm)	Overall Length (mm)	Catheter Size (Fr)
32	26-29	20	16	118	22
36	30-32			120	25
40	33-36				
46	37-42				

Table 1. Thoracic bifurcation dimensions

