4.4.2 Eligibility Criteria

Primary Study Arm

Inclusion Criteria

- A patient may be entered into the study if the patient has at least one of the following:
 - An aneurysm with a maximum diameter of greater than or equal to 5.5 cm or 2 times the normal diameter just proximal to the aneurysm using orthogonal (i.e., perpendicular to the centerline) measurements
 - Aneurysm with a history of growth greater than or equal to 0.5 cm in 6 months
 - Saccular aneurysm deemed at significant risk for rupture
 - Symptomatic aneurysm greater than or equal to 4.5 cm
- Axillary or brachial and iliac or femoral access vessel morphology that is compatible with vascular access techniques, devices or accessories, with or without use of a surgical conduit
- Proximal landing zone for the thoracic bifurcation stent graft that has:
 - Greater than or equal to 2.5 cm of non-aneurysmal aortic segment including previously placed graft material (neck) distal to the left subclavian artery (LSA) and diameter in the range of 26-42 mm

- Adequate distance from the celiac artery, in order to accommodate cannulation from the antegrade access point when considering the total deployed length of the thoracic bifurcation and visceral manifold
- Iliac artery or aortic distal fixation site, including both native tissue and previously placed graft, greater than or equal to 15 mm in length and diameter in the range of 8 – 25 mm
- Age: greater than or equal to 18 years old
- Life expectancy: greater than 1 year

Exclusion Criteria

General exclusion

- Patient is a good candidate for and elects for open surgical repair
- Can be treated in accordance with the instructions for use with a legally marketed endovascular device
- Is eligible for enrollment in a manufacturer-sponsored IDE at the investigational site
- Unwilling to comply with the follow-up schedule
- Inability or refusal to give informed consent
- Urgent or emergent presentation
- Patient is pregnant or breastfeeding
- Patient has a contained rupture
- Patient has a ruptured aneurysm
- Patient has a dissection in the portion of the aorta intended to be treated
- Obstructive stenting of any or all of the visceral vessels

- Poor performance status including two major system failures (including but not limited to cardiovascular, pulmonary, renal, hepatobiliary, and neuromuscular)

Medical exclusion criteria

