4.5.1.3 Performance related risks

There are performance risks of the modular components succumbing to material fatigue resulting in component separation, endoleak or endotension, graft occlusion, kinking, or migration. These risks can be mitigated several ways including adhering to industry standard seal zone lengths,

proper oversizing, lining branch stents with self-expanding stents, regular follow-ups to identify early evidence of migration or separation and allow for appropriate treatment, by the use of completion angiography coupled with cuffs, ballooning, or additional stent grafts if evidence of endoleak.

4.5.1.4 Actual Risk Realized While the stent graft design is intuitive, there is a learning curve with respect to the procedural considerations, necessary site infrastructure and post-operative management of patients treated with an endovascular TAAA therapy. During initial enrollment, actual risks observed include but were not limited to renal injury/failure, respiratory failure, paraplegia, and all-cause mortality. Although these risks are considered anticipated, the events are serious in nature and thus warrant investigation and consideration of appropriate corrective and preventative actions. The exact cause of each event and sequela of events within a given subject are difficult to extrapolate; however, lessons were learned during the first four cases in this series.

The target patient population of this study can represent challenges such as advanced age, presence of significant co-morbidities, and in some cases complex aortic anatomy. Anatomical challenges may influence operative variables (i.e. procedure time, blood loss, fluoroscopy time, and contrast volume) which may further exacerbate baseline co-morbidities and impact post-operative outcomes. The first four subjects treated under the study each presented baseline and operative challenges that may have affected outcome. From these experiences, lessons were learned, and mitigation strategies aimed to reduce risks identified.

With respect to the actual risks observed, several mitigation strategies will be implemented from patient selection, procedural considerations and site infrastructure perspectives. Procedural complexity is amplified substantially by arch anatomy either from right upper extremity access or from a type III arch with left upper extremity access, limiting subject selection. Parallax alterations are frequent and

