 - Standardized staging protocol aligned across parallel PS-IDEs
 - Adherence to the investigation protocol and clinical methods for case planning, , and implantation will be followed.
 - Patients will be carefully monitored throughout the study period.
 - The investigator will evaluate the adverse events during the course of the study.
 - Safety and effectiveness will be shared with additional Investigators to increase understanding of device and potential adverse events

- Independent DMC to evaluate subject health, device performance, and identify safety concerns regarding subject well-being

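### The 10-15% oversizing rule for the thoracic bifurcation cannot be met over most of the eligible 26-42 mm range with the sizes in Table 1

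*Combined protocol and SAP*

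**What the plan says.** Three parts of the protocol set the size of the thoracic bifurcation.

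- **Sizing rule (4.4.5.1, item 2):** "The diameter of the thoracic bifurcation stent graft should be 10-15% larger than the diameter of the aorta".
- **Size table (3.6, Table 1):** four proximal diameters, each with its vessel range: 32 mm for 26-29 mm, 36 mm for 30-32 mm, 40 mm for 33-36 mm and 46 mm for 37-42 mm. The same section counts the proximal end of this component among the critical sizing steps and has the operator choose from the available sizes.
- **Eligibility (4.4.2):** the proximal neck must lie "distal to the left subclavian artery (LSA) and diameter in the range of 26-42 mm". The synopsis and the intended-use statements in 3.6 and 4.2 give the same limits.

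The risk sections then rely on sizing. Section 4.5.1.3 lists "proper oversizing, lining branch stents with self-expanding stents" among the mitigations for endoleak, migration and related failures. Section 4.5.2 lists "Adherence to the investigation protocol and clinical methods for case planning" as a way of minimizing risk.

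**The concern.** The outer limits of Table 1 match the eligibility range, but the pairs inside the table do not appear to respect the 10-15% rule. If so, an operator with an eligible patient often cannot satisfy both. For many diameters, departing from the table would not help either, because no other listed size complies.

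Three things depend on this:

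- **Risk mitigation.** Section 4.5.1.3 relies on proper oversizing. I found no numerical statement of what that means for this component other than item 2 of 4.4.5.1.
- **Suitability.** Screening under 4.4.5 uses CT to judge whether vessel diameters suit the system. The answer depends on whether the table or the percentage is applied.
- **Deviations.** Section 4.7 requires prior IRB and FDA approval for deviations that may affect soundness or safety. The protocol does not say whether an implant that follows Table 1 but falls outside 10-15% is a deviation.

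There is also a link to the results. Secondary intervention for migration or for Type I or III endoleak counts against treatment success, the primary effectiveness endpoint (4.4.3).

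**Working it through.** **Inputs.** Rule: 10% to 15% above the aortic diameter (4.4.5.1). Graft sizes and vessel ranges: Table 1 (3.6). Eligible range: 26 to 42 mm (4.4.2).

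**Step 1: does Table 1 reproduce 10-15%?** Oversizing = graft diameter / aortic diameter − 1, taken at both ends of each range.

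| Graft (mm) | Smallest vessel | Oversizing | Largest vessel | Oversizing |
|---|---|---|---|---|
| 32 | 26 | 32/26 − 1 = 23.1% | 29 | 32/29 − 1 = 10.3% |
| 36 | 30 | 36/30 − 1 = 20.0% | 32 | 36/32 − 1 = 12.5% |
| 40 | 33 | 40/33 − 1 = 21.2% | 36 | 40/36 − 1 = 11.1% |
| 46 | 37 | 46/37 − 1 = 24.3% | 42 | 46/42 − 1 = 9.5% |

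It does not. The table spans 9.5% to 24.3%, and the smallest vessel in every row exceeds 15%.

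**Step 2: which diameters comply with any of the four sizes?** For each graft the compliant aortic window runs from graft/1.15 to graft/1.10.

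| Graft (mm) | Window (mm) | Width (mm) |
|---|---|---|
| 32 | 27.83 to 29.09 | 1.26 |
| 36 | 31.30 to 32.73 | 1.42 |
| 40 | 34.78 to 36.36 | 1.58 |
| 46 | 40.00 to 41.82 | 1.82 |

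The unrounded widths sum to 6.09 mm. The eligible range is 42 − 26 = 16 mm, so 6.09/16 = 38% complies and 62% does not.

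**Step 3: whole millimetres.** Seven of 17 comply: 28, 29, 32, 35, 36, 40 and 41. Ten do not: 26, 27, 30, 31, 33, 34, 37, 38, 39 and 42. Nine of the ten are above 15% with the Table 1 graft (16.1% to 24.3%); only 42 mm is below 10%. Taking a neighbouring size does not rescue them. At 33 mm the 36 mm graft gives 9.1% and the 40 mm graft 21.2%. At 37 mm the 40 mm graft gives 8.1% and the 46 mm graft 24.3%.

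**Step 4: other readings.**

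- Any of the four sizes, ignoring the Table 1 ranges: the same 7 of 17 comply.
- Percentages rounded to whole numbers: 42 mm comes in, so 9 of 17 (53%) still fail.
- Oversizing taken relative to the graft instead of the aorta: 9 of 17 fail.
- Continuous scale restricted to the listed vessel ranges (3 + 2 + 3 + 5 = 13 mm): 4.91/13 = 38% complies.

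Every reading leaves 53% to 62% of the range without a compliant size.

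**The case against.** The best reply is that item 2 says *should*, so it is guidance. Table 1 assigns a graft to every whole millimetre from 26 to 42, and the eligibility range matches it. On that view a single sentence is out of step, and nobody is forced into a breach. Nor is oversizing an eligibility criterion in 4.4.2.

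There are further points on that side:

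- Section 4.4.5.3 allows proximal extension with other thoracic grafts, and 4.4.2 accepts previously placed graft material as landing zone. A rule stated relative to the aorta may not apply directly in those cases.
- Section 3.5.3 speaks of conservative oversizing in subacute dissection, which suggests that sizing is partly case-dependent.
- The device IFU and master file are not in the documents and may contain a sizing chart.
- Nothing in the documents shows that 9.5%, or 16% to 24%, leads to endoleak or migration.

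Some of this stands. No harm is shown. The external physician reviewer in 4.5.2 works from the CT scan, and the protocol does not say that this reviewer applies the 10-15% figure. The 42 mm miss is marginal.

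The rest does not remove the conflict. Guidance that cannot be followed over most of the eligible range still needs correcting. The extension and prior-graft provisions do not cover a native landing zone. A sizing chart in the IFU would be one more source to align.

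**Conclusion.** The concern holds. The stated 10-15% oversizing is incompatible with the protocol's own size table over most of the eligible range: 10 of 17 whole-millimetre diameters (9 of 17 with whole-percent rounding), or 62% on a continuous scale. The largest excess over the upper limit is 24.3% − 15% = 9.3 percentage points, at 37 mm.

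The result assumes that the four sizes in Table 1 are the only ones available and that the rule applies to a native landing zone. It describes diameters, not patients: the documents give no distribution of landing-zone diameters, and only 15 subjects are planned. It does not touch the sample size or the hypothesis test. What it shows is an inconsistency in a sizing rule that the protocol relies on for risk mitigation.

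**What to change.** Reconcile item 2 of 4.4.5.1, Table 1 in 3.6 and the 26-42 mm range (synopsis, 3.6, 4.2 and 4.4.2) so that all follow one stated sizing rule, checked with the manufacturer and against the IFU. State whether oversizing is measured relative to the aorta or to the graft, and how the rule applies when the graft lands in existing graft material. If some eligible diameters still have no compliant size, say so in the eligibility criteria and state whether implanting at such a diameter is a protocol deviation. Which figure is right is for the sponsor and manufacturer to settle.

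The cost is protocol wording and one manufacturer check. No change to the sample size or the statistical analysis is needed.

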4.4.5.2 Pre-operative procedures

The patient will be removed from anti-coagulants prior to surgery. The day of surgery the following labs will be taken:

- Complete blood count to evaluate white blood cells, hemoglobin, and platelets
- Basic metabolic panel to evaluate creatinine
- Prothrombin time (at physician discretion)
- Partial thromboplastin time (at physician discretion)
- Pregnancy test (for female patients of childbearing age)

Spinal Drain

- The use of a spinal drain is required for all non-staged procedures on subjects being treated for a Crawford Type I, II, III, or V thoracoabdominal aneurysm
 - In the case of prior spinal surgery or any reason that would put the patient at higher risk for complications, the use is at the physician's discretion
- The use of a spinal drain on staged procedures is at the physician's discretion

The patient will be treated with general anesthesia under standard medical practices along with placement of a lumbar drain when possible. The management of anesthesia and the lumbar drain will be performed by the staffed anesthesia team. Standard heparinization practices will be followed and active clotting time will be monitored throughout the procedure. The patient will be prepped in normal sterile fashion from the clavicle to mid-thigh. Additionally, contrast will be diluted 50/50 in saline to reduce contrast exposure. Radiation reduction procedures will be followed as allowed.

